## **Secondary endpoints**

### **The secondary endpoints**

- The prevalence of FACEs from each baseline (diagnosis, and start of treatment) to compare between Migalastat-treated, ERT-treated patients and non-treated patients
- The incidence of FACEs from each baseline (diagnosis, and start of treatment) to compare between Migalastat-treated, ERT-treated patients and non-treated patients

- Time to the first cardiac, cerebrovascular, and renal clinical event separately by each specific category (including death in these categories) from start of treatment or baseline
- Incidence of cardiac, cerebrovascular, and renal clinical events separately by each specific category (including death in these categories)
- Occurrence of cardiac, cerebrovascular, and renal clinical events separately by each specific category (including death in these categories)
- Annualized rate of change in eGFR based on the Chronic Kidney Disease Epidemiology Collaboration equation (eGFRCKD-EPI) over time to compare between Migalastat-treated, ERT, and untreated patients
- The prevalence and incidence of a clinically significant change in mGFR and/or eGFR (according to KDIGO guidelines rapid progression is defined as a sustained decline in eGFR of more than 5 ml/min/1.73 m^2 /yr) from each baseline (diagnosis, and start of treatment) to compare between Migalastat-treated, ERT-treated patients and non-treated pts
- The prevalence and incidence of micro (> 30 mg/g creatinine) or macroalbuminuria (> 300) by urinary albumin/creatinine ratio (ACR) or urinary 24 h protein excretion from each baseline (diagnosis, and start of treatment) to compare between Migalastat-treated, ERT-treated patients and non-treated pts

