3.2. Secondary Effectiveness Analysis

Secondary endpoints listed below will be assessed by evaluating migalastat-treated and untreated patients and/or migalastat-treated and ERT-treated patients:

- The prevalence of FACEs from each baseline (diagnosis, and start of treatment) in migalastat-treated, ERT-treated patients and untreated patients

- The incidence of FACEs from each baseline (diagnosis, and start of treatment in migalastat-treated, ERT-treated patients and untreated patients
- Time to the first cardiac, cerebrovascular, and renal clinical event separately by each specific category (including death in these categories) from baseline (diagnosis and start of each treatment) using Cox proportional hazards model and descriptive statistics.
- Incidence of cardiac, cerebrovascular, and renal clinical events separately by each specific category (including death in these categories)
- Occurrence of cardiac, cerebrovascular, and renal clinical events separately by each specific category (including death in these categories)
- Annualized rate of change in eGFR based on the Chronic Kidney Disease Epidemiology Collaboration equation (eGFR CKD-EPI) over time in migalastat-treated, ERT, and untreated patients . Analysis will also be performed by eGFR category at baseline if the counts are sufficient.
- The prevalence and incidence of a clinically significant change in mGFR and/or eGFR (according to KDIGO guidelines rapid progression is defined as a sustained decline in eGFR of more than 5 ml/min/1.73 m²/yr) from each baseline (diagnosis, and start of treatment) in migalastat-treated, ERT-treated patients and untreated patients.
- The prevalence and incidence of micro (> 30 mg/g creatinine) or macroalbuminuria (> 300) by urinary albumin/creatinine ratio (ACR) or urinary 24 h protein excretion from each baseline (diagnosis, and start of treatment) in migalastat-treated, ERT-treated patients and untreated patients.

The analysis for the primary effectiveness endpoint will be performed at the 2-sided significance level of 0.05 to compare migalastat-treated and untreated patients. All other comparisons will also be done at the 2-sided significance level of 0.05 with no adjustment for multiple comparisons.

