11.2. Definition of the Migalastat or ERT Treatment Start or Treatment Switch

For analysis, if assessments were not collected on the treatment start date or a treatment switch date, then the assessment closest to the treatment start date will be utilized. If there are 2 assessments that are equidistant from the treatment start date, then the assessment prior to treatment start date will be utilized. Only assessments performed on that treatment will be used.

Treatment start date is used as the Analysis Start Date for comparing migalastat and ERT-treated patients. Diagnosis date is used as the Analysis Start Date for comparing migalastat and untreated patients.

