13.6. Secondary Endpoint: Prevalence of FACEs by Category

Prevalence of cardiac, cerebrovascular, and renal clinical events separately by each specific category (including death in these categories) will be analysed as in Section 13.3 for the composite FACEs.

13.7. Secondary Endpoint: Estimated Glomerular Filtration Rate to Compare Migalastat-treated, ERT Treated, and Untreated Patients

Estimated GFR will be summarized using descriptive statistics by treatment at diagnosis date. Descriptive statistics will be displayed for change from Analysis Start Date (time of diagnosis or treatment start) to e.g. time points such as the date of the first treatment switch, date of the treatment to migalastat or any other time points of interest.

For dialysis and transplant patients, the Analysis Start Date for eGFR will be reset to the last value before dialysis start or before transplantation and used thereafter.

Analysis Methods

Data will be listed. Listings will contain flags indicating therapy change. Spaghetti plots will indicate what treatment group a patient was on at the time of measurement.

Longitudinal analysis using Mixed Model for Repeated Measures (MMRM) will be used to analyze data over time. Trends over time using adjusted means will be plotted. Missing post-Analysis Start Date measurements will not be imputed as MMRM method allows for missing values. This analysis only accounts for changes over time regardless of therapy.

Covariates are:

- sex
- enrollment age as a continuous variable
- enrollment eGFR as a continuous variable
- proteinuria based on the UPCR value at enrollment
- LVMi at enrollment
- history of cardiac, cerebrovascular, and renal clinical events (a binary endpoint based on the composite event) prior to enrollment
- length of treatment for Fabry disease

If the measurements are not available, measurements prior to and closest to the Analysis Start Date will be used. In case that more than 50% of values are missing for a given covariate, it will be dropped from the analysis.

Additionally, the annualized rate of eGFR change will be calculated as the slope of the individual patients' regression equations over time. The annualized rate of change will be analyzed using t-test for migalastat-treated versus untreated patients. This analysis only accounts for changes over time regardless of therapy.

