An alternative analysis will only utilize data from periods on migalastat treatment and separately on the ERT treatment, and untreated periods.

13.8. Secondary Endpoints: Prevalence and Incidence of Clinically Significant change in mGFR or eGFR

The prevalence and incidence of a clinically significant change in mGFR and/or eGFR (according to KDIGO guidelines rapid progression is defined as a sustained decline in eGFR of more than 5 ml/min/1.73 m² /yr) from each baseline (diagnosis and start of treatment) to compare between migalastat-treated, ERT-treated patients and untreated patients will be analyzed using same methodology as for incidence and prevalence of FACEs.

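### The two eGFR analyses specified in SAP 13.7 disregard therapy, so they do not deliver the three-group comparison the endpoint promises; the by-period analysis that could is left unspecified

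*SAP*

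**What the plan says.** The protocol lists, as a secondary endpoint, the annualized rate of change in eGFR "over time to compare between Migalastat-treated, ERT, and untreated patients". SAP 3.2 repeats it "over time in migalastat-treated, ERT, and untreated patients", and the SAP 13.7 heading is "Estimated Glomerular Filtration Rate to Compare Migalastat-treated, ERT Treated, and Untreated Patients".

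SAP 13.7 then specifies two inferential analyses.

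- A mixed model for repeated measures with seven covariates: sex, age, eGFR, proteinuria, LVMi, history of clinical events, and "length of treatment for Fabry disease". Neither treatment group nor treatment-by-time is listed.
- A regression slope for each patient, followed by a test: "The annualized rate of change will be analyzed using t-test for migalastat-treated versus untreated patients". No ERT contrast is named.

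Each is followed by the same statement: "This analysis only accounts for changes over time regardless of therapy".

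The section closes with one further sentence: "An alternative analysis will only utilize data from periods on migalastat treatment and separately on the ERT treatment, and untreated periods". No model, time origin or between-group contrast is given for it.

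On the origin, SAP 11.2 says: "Diagnosis date is used as the Analysis Start Date for comparing migalastat and untreated patients". SAP 2 states that every patient is treatment naïve at diagnosis.

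**The concern.** The endpoint asks whether eGFR declines at different rates under three treatment states. A model without a treatment term cannot answer that, whatever the switching pattern. The slope test does form two groups. But with diagnosis as the origin and no cut at a switch, one patient's slope can run across untreated, ERT and migalastat years. The difference between groups is then a blend.

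What is at stake is a named secondary endpoint. Followed literally, the plan gives no treatment contrast from the mixed model, no ERT slope contrast at all, and a migalastat-untreated contrast of unknown dilution. The one analysis that fits the question would have to be designed after the data are in hand. SAP 15.6 (laboratory tests) and 16.9 (patient-reported outcomes) also borrow the 13.7 method.

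**Working it through.** The documents give no effect size, slope SD, group sizes or power for eGFR, so there is no planned figure to reproduce. The check has two parts.

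**What each analysis can estimate**

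- Mixed model: a time trend adjusted for seven covariates. Length of treatment does not separate migalastat from ERT and is not a treatment-by-time term. Result: no treatment contrast.
- Slope t-test: migalastat minus untreated, with switcher labels undefined. Result: no ERT contrast, and possible mixing.
- By-period alternative: data split into the three states. Result: fits the endpoint, but has no stated model or contrast.
- For comparison, the primary time-to-event analysis (SAP 13.1.1) censors untreated patients when they start therapy, and treated patients 30 days after a stop or switch. The two specified eGFR analyses have no such rule.

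**How much a whole-follow-up slope can dilute a difference**

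Inputs from the documents: follow-up from 2001 (both documents); end of follow-up December 2022 (Protocol, Study workflow) or December 2023 (SAP 2); migalastat available from 2016 (Protocol, Rationale and background); visits yearly or every other year; patients untreated at diagnosis.

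Assumptions: 1 January 2016 as the earliest migalastat start; diagnosis at the start of the stated year; no ERT before migalastat; linear decline within each state; evenly spaced measurements; the comparison group stays untreated.

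Let the slope be b0 before migalastat and b1 on it, and let p be the share of follow-up on migalastat. One least-squares line through all the data has slope b0 + w(b1 − b0), with w = p²(3 − 2p). The comparator has slope b0, so the share of the true difference kept is w.

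| End of follow-up | Migalastat start | Diagnosis | Years on drug / total | p | w |
|---|---|---|---|---|---|
| 2022 | 2016 | 2001 | 7/22 | 0.318 | 0.24 |
| 2022 | 2016 | 2005 | 7/18 | 0.389 | 0.34 |
| 2022 | 2016 | 2009 | 7/14 | 0.500 | 0.50 |
| 2022 | 2016 | 2013 | 7/10 | 0.700 | 0.78 |
| 2022 | 2016 | 2016 | 7/7 | 1.000 | 1.00 |
| 2022 | 2018 | 2001 | 5/22 | 0.227 | 0.13 |
| 2022 | 2020 | 2001 | 3/22 | 0.136 | 0.05 |
| 2022 | 2020 | 2016 | 3/7 | 0.429 | 0.39 |
| 2023 | 2016 | 2001 | 8/23 | 0.348 | 0.28 |
| 2023 | 2016 | 2009 | 8/15 | 0.533 | 0.55 |

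First row in full: 0.318² × (3 − 0.636) = 0.101 × 2.364 = 0.24. A direct fit to annual points gives 0.249, and to two-yearly points 0.259. With assumed slopes of −3 and −1 mL/min/1.73 m² per year, the annual fit is −3 + 0.249 × 2 = −2.50, an apparent difference of 0.50 against a true 2.0.

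Averaged over diagnosis dates spread evenly from 2001 to the start year (end 2022), w is 0.54 for a 2016 start, 0.40 for 2018 and 0.25 for 2020.

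**If the initial-cohort rule is carried over**

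Migalastat slopes then hold almost no pre-treatment time, and the mixing moves to untreated patients who later start therapy. If they spend a share q of follow-up on therapy with the same effect, the share kept is 1 − q²(3 − 2q).

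- q = 0.3: 1 − 0.09 × 2.4 = 0.78.
- q = 0.5: 1 − 0.25 × 2 = 0.50.

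If both groups are mixed, little may remain: the 2001 case (0.239) with q = 0.3 (0.216) leaves 0.239 − 0.216 = 0.02.

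**The case against.** The best defence is that SAP 13.7 as a whole does not ignore therapy. It plans the by-period alternative, descriptive changes from diagnosis or treatment start to switch dates, and listings and plots that show therapy at each measurement. The protocol (Study treatment) groups switchers by current treatment, if possible with a new baseline. SAP 11.2 sets treatment start as the origin for migalastat versus ERT. This stands: a reader might infer that eGFR is never analysed by therapy, and the documents do not support that. It does not supply the missing model, origin or contrast. Nor does it change the order, in which the therapy-specific analysis is the alternative.

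A reader might also infer that untreated and ERT years are counted as migalastat years. SAP 13.7 does not say how a switcher is labelled. SAP 3.1, written for the primary endpoint, uses the initial treatment cohort, and SAP 5.2.1 counts patients who start therapy within 3 months as initially treated. On that reading the mixing is mainly in the untreated group. SAP 5.2.1 also allows assignment to change by analysis, so the text leaves both readings open.

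Finally, a reader might take the sections that reuse 13.7 to be equally therapy-blind. SAP 15.6 says its analysis follows actual exposure, and SAP 16.9 describes changes to each switch by treatment group. What carries over is the ambiguity.

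**Conclusion.** The defect stands on the wording alone. The two specified eGFR analyses cannot give the promised three-group comparison: one has no treatment term, the other omits ERT and has no rule for switchers, and the analysis that fits is unspecified.

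The size of the dilution is not established. The share of a true slope difference that is kept runs from about 5% to 100% when the comparator stays untreated, and from 78% to 50% under the initial-cohort reading with 30% to 50% of untreated follow-up on therapy. It may be tempting to say that the difference would be largely averaged out. That needs less than half of follow-up to be on migalastat, for example diagnosis before 2009 with a 2016 start and follow-up to the end of 2022. The documents give no distribution of diagnosis dates, start dates or group labels.

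This is a should-fix: a secondary endpoint is affected, the primary time-to-event analysis is not, and the by-period data are already planned for use.

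**What to change.** Rewrite SAP 13.7 as follows.

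1. Make the by-period analysis the main one for this endpoint: a linear mixed model on all eGFR values with time-varying treatment (migalastat, ERT, untreated), time on current treatment, and their interaction. Include the listed covariates, with eGFR and age taken at the start of each period where available, because enrolment values do not describe a patient when a later therapy starts. Use a random intercept and slope, with a stated simplification if the model does not converge; with about 115 patients seen yearly or every other year this may be needed.
2. Define the time origin and group label for patients who switch, and when a period ends.
3. Report the three slopes, and the migalastat-ERT and migalastat-untreated differences, with 95% confidence intervals.
4. Keep the therapy-blind mixed model and whole-follow-up slopes as descriptive.
5. Apply the same order where 13.7 is reused (15.6 and 16.9), in line with the actual-exposure statement in 15.6.
6. Reconcile the two follow-up end dates, December 2022 and December 2023, since they set the length of the last period.

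The cost is SAP text and one different model on data already being collected. The price is precision: each slope rests on fewer years.

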13.9. Secondary Endpoint: Prevalence and Incidence of micro – or Macroalbuminuria

The prevalence and incidence of micro (> 30 mg/g creatinine) or macroalbuminuria (> 300) by urinary albumin/creatinine ratio (ACR) or urinary 24 h protein excretion from each baseline (diagnosis, and start of treatment) to compare between migalastat-treated, ERT-treated patients and untreated patients will be analyzed using same methodology as for incidence and prevalence of FACEs.

Analysis by ACR categories will be performed if enough data are available.

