4. SAMPLE SIZE JUSTIFICATION

Approximately 115 patients with established Fabry Disease, estimated 2/3 female and 1/3 male.

Sample size was not determined statistically. All patients from Danish National Fabry Centre are included.

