12. SUBGROUP ANALYSIS

Subgroup analyses will be performed by forming subsets of patients from the Safety Population, the Primary and Secondary Effectiveness Populations such as:

- Age (≤ 40 , > 40 years). For the Safety Population, enrollment date will be used to determine a patient's age. For the Effectiveness Population, the age will be calculated utilizing Analysis Start Date, ie, diagnosis date for migalastat-treated versus untreated group comparison and start of treatment for migalastat-treated versus ERT-treated comparison.
- Sex (female versus male)
- Renal impairment (Normal [GFR > 90 mL/min/1.73 m 2], Mild [GFR ≥ 60 to 90 mL/min/1.73 m 2], Moderate [GFR ≥ 30 to 60 mL/min/1.73 m 2], Severe [GFR < 30 mL/min/1.73 m 2]). For the Safety Population, enrollment date will be used to determine patient's eGFR. For the Primary and Secondary Effectiveness Populations, the eGFR will be calculated utilizing Analysis Start Date, ie, enrollment date for migalastat-treated versus untreated group comparison and start of treatment for migalastat-treated versus ERT-treated comparison.
- Proteinuria categories based on UPCR (< 0.5 g/g, 0.5 to 1.0 g/g, > 1.0 g/g)
- Classic phenotype in males versus non-classic phenotype (all others: males and females). In males, the classic phenotype of Fabry disease is determined by residual α -Gal A enzyme activity that is minimal or absent (ie, less than 5% of mean normal) and typified by earlier age of onset and more severe symptoms with multiple organ involvement, whereas the non-classic phenotype has residual α -Gal A activity and a later onset, but also is associated with significant disease progression. Use of α -Gal A in the determination of phenotype is applicable to treatment-naïve males only.
- Treatment-naïve ERT-treated versus treatment-naïve migalastat-treated. Treatment-naïve ERT patients are Fabry treatment-naïve patients at the start of ERT. Treatment-naïve migalastat patients are Fabry treatment-naïve patients at the start of migalastat.
- Male patients who have enzyme activity assessment at baseline

For some of the subgroups, only descriptive statistics will be provided due to a small subgroup size.

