15.6. Clinical Laboratory Tests

Analyses of clinical laboratory assessments will focus on serum creatinine, urine protein, urine albumin, and urine ACR. Other labs results will be provided in by-patient listings. Analysis will be done using the same methodology as for eGFR (Section 13.7).

Data will be summarized using descriptive statistics will be displayed for change from Analysis Start Date (time of diagnosis or treatment start) to e.g. time points such as the date of the first treatment switch, date of the treatment to migalastat or any other time points of interest.

Analysis Methods

Data will be listed. Listings will contain flags indicating therapy change. Spaghetti plots will indicate what treatment group a patient was on at the time of measurement.

In the Safety Population, data will be analyzed from the time of diagnosis.

For dialysis and transplant patients, the Analysis Start Date creatinine (as it is done for eGFR in Section 13.7) will be reset to the last value before dialysis start or before transplantation and used thereafter.

All laboratory data, values, units, normal reference range, and out-of-range flags collected in the clinical database will be included in by-patient listings for further medical review.

The analysis will address data based on the actual exposure. The count of out of range values as well as counts of clinically significant results will be presented by treatment.

Summaries of out of range values and shift tables (using Analysis Start Date as baseline) could be prepared for timepoints of interest such as e.g. start of migalastat therapy. .

An additional table showing if a test result was out of range at any measurement over time will be prepared. A similar table will be prepared for potentially clinically significant values.

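### The albuminuria endpoint ties one pair of albumin cut-offs to either ACR or 24-h total protein, so a patient's status depends on which test was done

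*SAP*

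**What the plan says.** SAP 13.9 sets microalbuminuria at above 30 mg/g creatinine and continues with "macroalbuminuria (> 300) by urinary albumin/creatinine ratio (ACR) or urinary 24 h protein excretion from each baseline". The baselines are diagnosis and start of treatment, and the comparison is between migalastat-treated, ERT-treated and untreated patients. The methods are those used for prevalence and incidence of FACEs. SAP 3.2 has the same definition, and so does the Protocol under Secondary endpoints ("by urinary albumin/creatinine ratio (ACR) or urinary 24 h protein excretion").

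The only unit given is mg/g creatinine, attached to 30. No separate cut-off for 24-h protein appears in either document, and neither says which test decides when a patient has both.

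Elsewhere albumin and protein are different variables. SAP 15.6 states: "Analyses of clinical laboratory assessments will focus on serum creatinine, urine protein, urine albumin, and urine ACR". The Protocol lists urine protein, urine albumin and ACR separately under Renal function and Safety Endpoints. Its table of exploratory outcome variables has ACR in mg/g and proteinuria in mg, with no 24-h albumin field.

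SAP 13.9 adds one further sentence: "Analysis by ACR categories will be performed if enough data are available".

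**The concern.** Two different quantities share one threshold. ACR measures albumin relative to creatinine. A 24-h protein excretion measures all urinary protein as an amount per day. A programmer following the text must either apply 30 and 300 to protein in mg/24 h or choose a protein threshold that the plan does not contain. The first mixes two measures under one label. The second sets an endpoint definition after the retrospective data have been collected.

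The endpoint is explicitly comparative, and SAP 3.2 tests it without protection: "All other comparisons will also be done at the 2-sided significance level of 0.05 with no adjustment for multiple comparisons". If the share of patients classified by protein differs between treatment groups, that difference alone produces a difference in the apparent frequency of albuminuria. There is a plausible route for this. Follow-up starts in 2001 and migalastat was available only from 2016, so treatment is linked to calendar time, and choice of laboratory test may be as well.

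**Working it through.** The plan states no expected frequency or power for this endpoint (SAP 4: "Sample size was not determined statistically"), so there is no figure to reproduce. The check is unit arithmetic.

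**Inputs**
- Cut-offs c = 30 and 300 (Protocol secondary endpoints; SAP 3.2 and 13.9).
- Albumin share of total urinary protein, f: not in the documents. Assumed 0.3 to 0.9.
- Daily creatinine excretion, C: not in the documents. Assumed 0.5 to 2.0 g/day.

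**Step 1: like units.** Albumin = f × protein.

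| f | albumin in 30 mg protein | albumin in 300 mg protein | protein containing 300 mg albumin |
|---|---|---|---|
| 0.3 | 9 mg | 90 mg | 300/0.3 = 1000 mg |
| 0.5 | 15 mg | 150 mg | 300/0.5 = 600 mg |
| 0.7 | 21 mg | 210 mg | 300/0.7 = 429 mg |
| 0.9 | 27 mg | 270 mg | 300/0.9 = 333 mg |

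Albumin cannot exceed total protein. So everyone above a cut-off by albumin is also above it by protein, and for any f below 1 the protein route can add patients whose albumin is below it.

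**Step 2: the units the plan actually mixes.** For 24-h protein P in mg, the implied ACR in mg/g is f × P / C. At P = 300:
- C = 1.0: 0.3 × 300 / 1.0 = 90 to 0.9 × 300 / 1.0 = 270 mg/g
- C = 2.0: 0.3 × 300 / 2.0 = 45 to 0.9 × 300 / 2.0 = 135 mg/g
- C = 0.5: 0.3 × 300 / 0.5 = 180 to 0.9 × 300 / 0.5 = 540 mg/g

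The protein route over-calls relative to ACR whenever f is numerically below C. In a patient with low creatinine excretion the unit mismatch can offset or reverse this. In either case the same patient can be positive on one test and negative on the other.

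**Step 3: effect on a comparison.** Let a be the proportion positive by ACR, b the proportion positive by protein, and p the fraction of a group classified by protein. Observed frequency = (1 − p)a + pb. For two groups with the same a and b, the spurious difference is (p₁ − p₂)(b − a). For illustration only, take a = 35% and b = 95%, all inputs assumed:
- p₁ = 0.3, p₂ = 0: 0.7 × 35% + 0.3 × 95% = 53% against 35%, a difference of +18 points
- p₁ = p₂: 0
- p₁ = 0, p₂ = 0.3: −18 points

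With p₁ = 0.1 and p₂ = 0, the first case becomes 0.9 × 35% + 0.1 × 95% = 41%. With b = 60%, the 30% and 10% cases become 42.5% and 37.5%. The documents give none of a, b or p by group, so neither sign nor size can be fixed.

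**The case against.** **The text does not expressly apply 30/300 to protein.** This is fair. With mg/g as the only unit and none on 300, the protein criterion can equally be called undefined. An undefined criterion still has to be written before analysis.

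**The plan already has an ACR analysis.** SAP 13.9 foresees one by ACR category, and SAP 15.6 analyses protein, albumin and ACR separately. But the ACR-category analysis is conditional on enough data, gives no protein threshold and does not define the endpoint.

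**It is one secondary endpoint among several.** This is true, and it limits the weight of the point.

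Two stronger readings are tempting, and the documents support neither.

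- *That SAP 12 contradicts SAP 13.9.* SAP 12 lists "Proteinuria categories based on UPCR (< 0.5 g/g, 0.5 to 1.0 g/g, > 1.0 g/g", and 0.3 g/g lies in its lowest band. But that band is a subgroup split and is not labelled normal. A correctly measured ACR of 30 mg/g also falls there (at f = 0.5, UPCR = 30/0.5 = 60 mg/g). Placing 300 mg/24 h in the band needs creatinine excretion above 300/500 = 0.6 g/day, a figure the documents do not supply.
- *That the comparison is tilted towards migalastat.* This would need protein testing to be concentrated in untreated and ERT periods. Nothing says when each test was used, and untreated and ERT patients are also followed to the end of the study.

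**Conclusion.** The point holds as a defect of definition. One pair of albumin cut-offs serves two measures with different analytes and different units, in all three places where the endpoint is defined, with no protein threshold and no precedence rule. The mismatch follows from the text and from albumin being part of protein. Its size rests on assumptions: at f between 0.3 and 0.9, 300 mg of protein holds 90 to 270 mg of albumin. The over-call holds in like units, and across mg/24 h and mg/g wherever f is numerically below creatinine excretion in g/day.

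Between-group bias is conditional on the test mix differing by treatment, and its direction and size are unknown. Even with an equal mix, each group's prevalence and incidence combine two measures. The correction should be made before analysis. The primary endpoint is not touched.

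**What to change.** In the Protocol's secondary endpoints and in SAP 3.2 and 13.9:

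1. Define micro- and macroalbuminuria by ACR only, with mg/g creatinine stated for both: above 30 and up to 300 for micro, above 300 for macro.
2. Do not apply 30 or 300 to 24-h protein. Report patients with only 24-h protein separately, in mg/24 h. Use the SAP 12 UPCR categories for them only where urine creatinine allows a UPCR to be calculated.
3. Tabulate, by treatment period, how many patients were classified by each test.

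The cost is wording in three places, a separate protein table and the tabulation of test type. The downside is that patients with only 24-h protein leave the albuminuria endpoint. If those patients cluster in particular treatment periods the loss is not neutral, and the tabulation in step 3 lets a reader see that.
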